## 13 TRIAL MANAGEMENT

### 13.1 Data and Safety Monitoring Plan (DSMP)

The study will be conducted with guidance from the Tisch Cancer Institute Cancer Center's DSMP.

HCRN oversight activities include:

- Review and process all adverse events requiring expedited reporting as defined in the protocol
- Provide trial accrual progress, safety information, and data summary reports to the sponsor-investigator
- Submit data summary reports at least every 6 months to the DSMC for review according to the Tisch Cancer Institute Cancer Center's DSMP

### 13.2 Tisch Cancer Institute Cancer Center Data Safety Monitoring Committee

**HCRN will provide the following for the DSMC to review:**

- Adverse event summary report
- Audit results, if applicable
- Data related to stopping/decision rules described in study design
- Study accrual patterns
- Protocol deviations

The DSMC will review study data at least every 6 months. Documentation of DSMC reviews will be provided to sponsor-investigator and HCRN. Issues of immediate concern by the DSMC will be brought to the attention of the sponsor-investigator and other regulatory bodies as appropriate. The sponsor-investigator will work with HCRN to address the DSMC's concerns.

### 13.3 Data Quality Oversight Activities

Remote validation of EDC system data will be completed on a continual basis throughout the life cycle of the study. Automated edit check listings will be used to generate queries in the EDC system and transmitted to the site to address in a timely fashion. Corrections will be made by the study site personnel.

Participating sites may also be subject to quality assurance audits by AstraZeneca-MedImmune or its designee as well as inspection by appropriate regulatory agencies.

#### 13.3.1 Onsite Monitoring

Monitoring visits to the trial sites may be made periodically during the trial to ensure key aspects of the protocol are followed. Selected source documents will be reviewed for verification of agreement with data entered into the EDC system. It is important for the site investigator and their relevant personnel to be available for a sufficient amount of time during the monitoring visits or audit, if applicable. The site investigator and institution guarantee access to source documents by HCRN or its designee.

### **13.4 Compliance with Trial Registration and Results Posting Requirements**

Under the terms of the Food and Drug Administration Modernization Act (FDAMA) and the Food and Drug Administration Amendments Act (FDAAA), the sponsor-investigator of the trial is solely responsible for determining whether the trial and its results are subject to the requirements for submission to the Clinical Trials Data Bank, <http://www.clinicaltrials.gov>. All results of primary and secondary objectives must be posted to CT.gov within a year of completion. The sponsor-investigator has delegated responsibility to HCRN for registering the trial and posting the results on clinicaltrials.gov. Information posted will allow subjects to identify potentially appropriate trials for their disease conditions and pursue participation by calling a central contact number for further information on appropriate trial locations and study site contact information.

## **14. DATA HANDLING AND RECORD KEEPING**

### **14.1 Data Management**

HCRN will serve as the Clinical Research Organization for this trial. Data will be collected through a web based clinical research platform, a system compliant with Good Clinical Practices and Federal Rules and Regulations. HCRN personnel will coordinate and manage data for quality control assurance and integrity. Select data will be collected and entered into the EDC system by study site personnel from participating institutions.

### **14.2 Case Report Forms and Submission**

Generally, clinical data will be electronically captured in the EDC system and correlative results will be captured in the EDC system or other secure database(s). If procedures on the study calendar are performed for standard of care, at minimum, that data will be captured in the source document. Select standard of care data will also be captured in the EDC system, according to study-specific objectives.

The completed dataset is the sole property of the sponsor-investigator's institution and should not be exported to third parties, except for authorized representatives of appropriate Health/Regulatory Authorities, without permission from the sponsor-investigator and HCRN.

### **14.3 Record Retention**

To enable evaluations and/or audits from Health Authorities/HCRN, the site investigator agrees to keep records, including the identity of all subjects (sufficient information to link records; e.g., hospital records), all original signed informed consent forms, copies of all source documents, and detailed records of drug disposition. All source documents are to remain in the subject's file and retained by the site investigator in compliance with the site contract with HCRN. No records will be destroyed until HCRN confirms destruction is permitted.

### **14.4 Confidentiality**

There is a slight risk of loss of confidentiality of subject information. All records identifying the subjects will be kept confidential and, to the extent permitted by the applicable laws and/or regulations, will not be made publicly available. Information collected will be maintained on secure, password protected electronic systems. Paper files that contain personal information will be kept in locked and secure locations only accessible to the study site personnel. Subjects will

be informed in writing that some organizations including the sponsor-investigator and his/her research associates, HCRN, AstraZeneca, IRB, or government agencies, like the FDA, may inspect their medical records to verify the information collected, and that all personal information made available for inspection will be handled in strictest confidence and in accordance with local data protection laws.

If the results of the study are published, the subject's identity will remain confidential.

## **15 ETHICS**

### **15.1 Institutional Review Board (IRB) Approval**

The final study protocol and the final version of the informed consent form must be approved in writing by an IRB. The site investigator must submit written approval by the IRB to HCRN before he or she can enroll subjects into the study.

The site investigator is responsible for informing the IRB of any amendment to the protocol in accordance with local requirements. In addition, the IRB must approve all advertising used to recruit subjects for the study. The protocol must be re-approved by the IRB, as local regulations require.

Progress reports and notifications of serious and unexpected adverse events will be provided to the IRB according to local regulations and guidelines.

### **15.2 Ethical Conduct of the Study**

The study will be performed in accordance with ethical principles originating from the Declaration of Helsinki. Conduct of the study will be in compliance with ICH Good Clinical Practice, and with all applicable federal (including 21 CFR parts 56 & 50), state, or local laws.

### **15.3 Informed Consent Process**

The site investigator will ensure the subject is given full and adequate oral and written information about the nature, purpose, possible risks and benefits of the study. Subjects must also be notified they are free to discontinue from the study at any time. The subject should be given the opportunity to ask questions and allowed time to consider the information provided.

The subject's signed and dated informed consent must be obtained before conducting any procedure specifically for the study. The site investigator must store the original, signed informed consent form. A copy of the signed informed consent form must be given to the subject.

| 
Drug administration modifications of study drug/study regimen will be made to manage potential immune-related AEs based on severity of treatment-emergent toxicities graded per NCI CTCAE v4.03.
 
In addition to the criteria for permanent discontinuation of study drug/study regimen based on CTC grade/severity (table below), permanently discontinue study drug/study regimen for the following conditions:
 
 
• Inability to reduce corticosteroid to a dose of <math>\leq 10</math> mg of prednisone per day (or equivalent) within 12 weeks after last dose of study drug/study regimen
 
• Recurrence of a previously experienced Grade 3 treatment-related AE following resumption of dosing
 
 
Grade 1      No dose modification
 
Grade 2      Hold study drug/study regimen dose until Grade 2 resolution to Grade <math>\leq 1</math>.
 
If toxicity worsens, then treat as Grade 3 or Grade 4.
 
Study drug/study regimen can be resumed once event stabilizes to Grade <math>\leq 1</math> after completion of steroid taper.
 
Patients with endocrinopathies who may require prolonged or continued steroid replacement can be retreated with study drug/study regimen on the following conditions:
 
 
1. The event stabilizes and is controlled.
 
2. The patient is clinically stable as per Investigator or treating physician's clinical judgement.
 
3. Doses of prednisone are at <math>\leq 10</math> mg/day or equivalent.
 
 | 
It is recommended that management of immune-mediated adverse events (imAEs) follows the guidelines presented in this table:
 
 
– It is possible that events with an inflammatory or immune mediated mechanism could occur in nearly all organs, some of them not noted specifically in these guidelines.
 
– Whether specific immune-mediated events (and/or laboratory indicators of such events) are noted in these guidelines or not, patients should be thoroughly evaluated to rule out any alternative etiology (e.g., disease progression, concomitant medications, and infections) to a possible immune-mediated event. In the absence of a clear alternative etiology, all such events should be managed as if they were immune related. General recommendations follow.
 
– Symptomatic and topical therapy should be considered for low-grade (Grade 1 or 2, unless otherwise specified) events.
 
– For persistent (<math>>3</math> to 5 days) low-grade (Grade 2) or severe (Grade <math>\geq 3</math>) events, promptly start prednisone 1 to 2 mg/kg/day PO or IV equivalent.
 
– Some events with high likelihood for morbidity and/or mortality – e.g., myo-carditis, or other similar events even if they are not currently noted in the guidelines – should progress rapidly to high dose IV corticosteroids (methylprednisolone at 2 to 4 mg/kg/day) even if the event is Grade 2, and if clinical suspicion is high and/or there has been clinical confirmation. Consider, as necessary, discussing with the study physician, and promptly pursue specialist consultation.
 
– If symptoms recur or worsen during corticosteroid tapering (28 days of taper), increase the corticosteroid dose (prednisone dose [e.g., up to 2 to 4 mg/kg/day PO or IV equivalent]) until stabilization or improvement of symptoms, then resume corticosteroid tapering at a slower rate (<math>>28</math> days of taper).
 
– More potent immunosuppressives such as TNF inhibitors (e.g., infliximab) (also refer to the individual sections of the imAEs for specific type of immunosuppressive) should be considered for events not responding to systemic steroids. Progression to use of more potent immunosuppressives should proceed more rapidly in events with high likelihood for morbidity and/or mortality – e.g., myocarditis, or other similar events even if they are not currently noted in the guidelines – when these events are not responding to systemic steroids.
 
– With long-term steroid and other immunosuppressive use, consider need for Pneumocystis jirovecii pneumonia (PJP, formerly known as Pneumocystis carinii pneumonia) prophylaxis, gastrointestinal protection, and glucose monitoring.
 
 |

## Dosing Modification and Toxicity Management Guidelines for Immune-Mediated, Infusion-Related, and Non-Immune-Mediated Reactions

### General Considerations

| Dose Modifications   |  | Toxicity Management   |
|--|--|---|
| Grade 3
Depending on the individual toxicity, study drug/study regimen may be permanently discontinued. Please refer to guidelines below.  |  | – Discontinuation of study drug/study regimen is not mandated for Grade 3/Grade 4 inflammatory reactions attributed to local tumor response (e.g., inflammatory reaction at sites of metastatic disease and lymph nodes). Continuation of study drug/study regimen in this situation should be based upon a benefit-risk analysis for that patient. |
| Grade 4
Permanently discontinue study drug/study regimen.

Note: For Grade $\geq 3$ asymptomatic amylase or lipase levels, hold study drug/study regimen, and if complete work up shows no evidence of pancreatitis, study drug/study regimen may be continued or resumed.

Note: Study drug/study regimen should be permanently discontinued in Grade 3 events with high likelihood for morbidity and/or mortality – e.g., myocarditis, or other similar events even if they are not currently noted in the guidelines. Similarly, consider whether study drug/study regimen should be permanently discontinued in Grade 2 events with high likelihood for morbidity and/or mortality – e.g., myocarditis, or other similar events even if they are not currently noted in the guidelines – when they do not rapidly improve to Grade $<1$ upon treatment with systemic steroids and following full taper

Note: There are some exceptions to permanent discontinuation of study drug for Grade 4 events (i.e., hyperthyroidism, hypothyroidism, Type 1 diabetes mellitus). |  |   |

AE Adverse event; CTC Common Toxicity Criteria; CTCAE Common Terminology Criteria for Adverse Events; imAE immune-mediated adverse event; IV intravenous; NCI National Cancer Institute; PO By mouth.

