| Endocrinopathy

(e.g., hyperthyroidism, hypothyroidism, Type 1 diabetes mellitus, hypophysitis, hypopituitarism, and adrenal insufficiency; exocrine event of amylase/lipase increased also included in this section) | Any Grade

(depending on the type of endocrinopathy, refer to NCI CTCAE v4.03 for defining the CTC grade/severity) | General Guidance               | For Any Grade: 
 
– Consider consulting an endocrinologist for endocrine events.
 
– Consider, as necessary, discussing with study physician.
 
– Monitor patients for signs and symptoms of endocrinopathies. Non-specific symptoms include headache, fatigue, behavior changes, changed mental status, vertigo, abdominal pain, unusual bowel habits, polydipsia, polyuria, hypotension, and weakness.
 
– Patients should be thoroughly evaluated to rule out any alternative etiology (e.g., disease progression including brain metastases, or infections).
 
– Depending on the suspected endocrinopathy, monitor and evaluate thyroid function tests: TSH, free T3 and free T4 and other relevant endocrine and related labs (e.g., blood glucose and ketone levels, HgA1c).
 
– For modest asymptomatic elevations in serum amylase and lipase, corticosteroid treatment is not indicated as long as there are no other signs or symptoms of pancreatic inflammation.
 
– If a patient experiences an AE that is thought to be possibly of autoimmune nature (e.g., thyroiditis, pancreatitis, hypophysitis, or diabetes insipidus), the investigator should send a blood sample for appropriate autoimmune antibody testing.
 
 |
| Grade 1   | No dose modifications.  |                                       | For Grade 1 (including those with asymptomatic TSH elevation): 
 
– Monitor patient with appropriate endocrine function tests.
 
– For suspected hypophysitis/hypopituitarism, consider consultation of an endocrinologist to guide assessment of early-morning ACTH, cortisol, TSH and free T4; also consider gonadotropins, sex hormones, and prolactin levels, as well as
 
   |

|                     |   |   |
|---------------------|---|---|

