| Grade 3 or 4 | 
For Grade 3 or 4 endocrinopathy other than hypothyroidism and Type 1 diabetes mellitus, hold
   | 
For Grade 3 or 4:
 
 
– Consult endocrinologist to guide evaluation of endocrine function and, as indicated by suspected endocrinopathy and as
 
  |

|   |  |  |  |
|---|--|--|--|
|   |  | 
study drug/study regimen dose until endocrinopathy symptom(s) are controlled.
 
Study drug/study regimen can be resumed once event stabilizes and after completion of steroid taper.
 
Patients with endocrinopathies who may require prolonged or continued steroid replacement (e.g., adrenal insufficiency) can be retreated with study drug/study regimen on the following conditions:
 
 
1. The event stabilizes and is controlled.
 
2. The patient is clinically stable as per investigator or treating physician's clinical judgement.
 
3. Doses of prednisone are <math>\leq 10</math> mg/day or equivalent.
 
 | 
clinically indicated, consider pituitary scan. Hospitalization recommended.
 
 
– For all patients with abnormal endocrine work up, except those with isolated hypothyroidism or Type 1 DM, and as guided by an endocrinologist, promptly initiate empiric IV methylprednisolone 1 to 2 mg/kg/day or equivalent, as well as relevant hormone replacement (e.g., hydrocortisone, sex hormones).
 
– For adrenal crisis, severe dehydration, hypotension, or shock, immediately initiate IV corticosteroids with mineralocorticoid activity.
 
– Isolated hypothyroidism may be treated with replacement therapy, without study drug/study regimen interruption, and without corticosteroids.
 
– Isolated Type 1 diabetes mellitus may be treated with appropriate diabetic therapy, without study drug/study regimen interruption, and without corticosteroids.
 
– Once patients on steroids are improving, gradually taper immunosuppressive steroids (as appropriate and with guidance of endocrinologist) over <math>\geq 28</math> days and consider prophylactic antibiotics, antifungals, and anti-PJP treatment (refer to current NCCN guidelines for treatment of cancer-related infections [Category 2B recommendation]).a
 
 |

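### Appendix 1 is inconsistent on Grade 4 hypophysitis, hypopituitarism and adrenal insufficiency: the General Considerations forbid further dosing that the endocrinopathy row permits

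*Combined protocol and SAP*

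**What the plan says.** Appendix 1 has two layers: a General Considerations table organised by grade, and a table of specific immune-mediated reactions organised by organ system.

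In the General Considerations, the Grade 4 instruction is "Permanently discontinue study drug/study regimen". A note to that instruction reads: "Note: There are some exceptions to permanent discontinuation of study drug for Grade 4 events (i.e., hyperthyroidism, hypothyroidism, Type 1 diabetes mellitus".

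In the table of specific reactions, the endocrinopathy row defines its scope by examples that include "hyperthyroidism, hypothyroidism, Type 1 diabetes mellitus, hypophysitis, hypopituitarism, and adrenal insufficiency". Grades 3 and 4 share one entry. For endocrinopathies other than hypothyroidism and Type 1 diabetes mellitus, that entry says to hold "study drug/study regimen dose until endocrinopathy symptom(s) are controlled". Dosing may resume once the event has stabilised and the steroid taper is complete. It continues: "Patients with endocrinopathies who may require prolonged or continued steroid replacement (e.g., adrenal insufficiency) can be retreated with study drug/study regimen on the following conditions". The conditions are a stable and controlled event, a clinically stable patient in the physician's judgment, and prednisone at no more than 10 mg/day or equivalent.

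Sections 6.2 and 6.4 make Appendix 1 the source of the rules for stopping treatment because of toxicity.

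**The concern.** For a Grade 4 hypophysitis, hypopituitarism or adrenal insufficiency, a site reading the general table finds that treatment ends. A site reading the endocrinopathy row finds that treatment is held and may restart. A site that restarts complies with one table and breaches the other.

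The main stake is patient safety. Hypophysitis and adrenal insufficiency are named tremelimumab risks in Section 10.1.4 and adverse events of special interest in Section 11.1.3, and the row itself provides for adrenal crisis and shock.

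The second stake is the safety record. Section 6 has subjects evaluated for adverse events that require interruption or discontinuation, and Section 6.4 records the reason for stopping on the eCRF. The same event could appear as a discontinuation for toxicity at one site and as an interruption at another. The monitoring committee also reviews protocol deviations (Section 13.2), and whether resumption is a deviation depends on the table used.

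**Working it through.** No arithmetic applies, and the plan states no figure to reproduce. The check is a comparison of the two tables, followed by a search for text that would settle any difference.

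**1. The six named endocrinopathies at Grade 4**

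| Event | General Considerations | Endocrinopathy row, Grade 3 or 4 | Compatible? |
|---|---|---|---|
| Hypothyroidism | Listed exception | If isolated, may be treated without interrupting study drug | Yes |
| Type 1 diabetes mellitus | Listed exception | If isolated, may be treated without interrupting study drug | Yes |
| Hyperthyroidism | Listed exception | Hold; may resume | Yes |
| Hypophysitis | Not listed, so permanent discontinuation | Hold; may resume | No |
| Hypopituitarism | Not listed, so permanent discontinuation | Hold; may resume | No |
| Adrenal insufficiency | Not listed, so permanent discontinuation | Hold; may resume; the row's example for further treatment | No |

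Three of the six conflict. This counts named conditions and is not an event rate. The row's list is given as examples, and the row also takes in raised amylase and lipase.

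**2. Do the other general exceptions cover the three events?** There are two. One concerns Grade 3 or higher "asymptomatic amylase or lipase levels, hold study drug/study regimen, and if complete work up shows no evidence of pancreatitis". The other says: "Discontinuation of study drug/study regimen is not mandated for Grade 3/Grade 4 inflammatory reactions attributed to local tumor response". Neither reaches hypophysitis, hypopituitarism or adrenal insufficiency.

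**3. Does the general table defer to the specific rows?** It does so at Grade 3: "Depending on the individual toxicity, study drug/study regimen may be permanently discontinued. Please refer to guidelines below". The Grade 4 instruction carries no such deferral. Sections 6.2 and 6.4 refer to Appendix 1 as a whole and do not rank its tables.

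**4. How do the other rows treat Grade 4?** Nine other rows give a Grade 4 action: pneumonitis, diarrhea/colitis, hepatitis, nephritis, rash, neurotoxicity, peripheral neuromotor syndromes, myocarditis and myositis. All nine require permanent discontinuation, as the general rule does. Endocrinopathy is the only row that departs from it. The exception note, which names only endocrine events, is therefore the text that would have to bring the two tables into line, and it covers part of the row only.

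**5. Is there a second mismatch on the same events?** Yes. The general table prints the permission to treat again during steroid replacement under Grade 2. The endocrinopathy row prints it under Grade 2 and again under Grade 3 or 4.

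**6. Does any statistical rule depend on the answer?** The Simon boundaries (0 responses in 18; 3 or more in 28) and the exact-binomial response analysis make no reference to this management rule. The toxicity rule in Section 12.7 counts treatment-related events of Grade 3 or higher, so a treatment-related Grade 4 event counts whether the drug is later stopped or resumed.

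**The case against.** The strongest reply is that the specific row governs. Each specific row states its own Grade 4 action, so the rows read as self-contained dosing instructions, and the endocrinopathy row names Grade 4 expressly. The exception note is also not a complete list, because the same General Considerations contain the two further exceptions in step 2. On this view many readers would simply apply the row. The reading is plausible, and it makes the fix a clarification. It is not stated anywhere, however. The note addresses endocrine exceptions directly and leaves these three out, and the only pointer to the rows stands under Grade 3.

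The second reply is that the protocol provides a way out. Section 6.2 tells the site investigator to consult the sponsor-investigator if in doubt, although the adjoining sentence concerns causality. Section 6.4 lets the site investigator change therapy in the subject's best interest. Section 11.1.3 presents the guidelines as an aid to clinical judgment, and the row calls for an endocrinology consult at Grade 3 or 4. These provisions stand and reduce the risk. It would be wrong to infer that Sections 6.2 and 6.4 do nothing beyond pointing to Appendix 1. None of these provisions ranks the tables, though, and a site that has read only one table has no reason to feel doubt.

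A reader might also infer that the tables give opposite orders. They do not. The hold is directive, but resumption is permitted under conditions and never required, so a site that stops permanently breaches neither table.

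**Conclusion.** The inconsistency is real and lies in the current text. For Grade 4 hypophysitis, hypopituitarism and adrenal insufficiency, the General Considerations forbid further dosing and the endocrinopathy row conditionally permits it, with no stated order of precedence. The conclusion rests on reading the exception note as written, and on taking the general Grade 4 rule to apply to endocrine events, which the note itself implies by exempting some of them.

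The practical size is small in numbers and serious per event. The documents give no rate for these events at Grade 4, so none is estimated. Few are expected in 28 patients, and sites could, not necessarily would, manage them differently. The effect on recorded data is limited to discontinuations and interruptions for toxicity. A reader might go further and infer that the safety endpoint is compromised because the number of doses received would vary. The documents do not support this: Sections 2.2.2, 12.2.2, 12.4 and 12.6.2 describe safety through CTCAE toxicity summarised in frequency tables and do not name doses received as a safety measure. The Simon design, the response analysis and the toxicity stopping rule stand as they are.

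This should be corrected, but it does not threaten the trial's primary conclusion.

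**What to change.** Reconcile the Grade 4 instruction and its exception note in the General Considerations with the Grade 3 or 4 entry of the endocrinopathy row, so that hypophysitis, hypopituitarism and adrenal insufficiency each have one stated Grade 4 action in both places. This can be done by aligning the exception list with the row or by separating Grade 3 from Grade 4 within the row. Alternatively, add one sentence to Appendix 1 saying which table prevails when they differ. The placement of the steroid-replacement permission should be checked in the same edit. Which action applies is for the sponsor-investigator and the drug supplier to decide; this review takes no position on it.

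The cost is a wording change in Appendix 1 at the next amendment, with no extra patients or procedures.
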